**LEVEL OF ETHICAL REVIEW:**

Indicate the [level of ethical review](#) that is being sought for this application:

	
Full HREC review
 
Applies to all research involving more than 'low risk research' as defined in the National Statement on Ethical Conduct in Human Research 2007 (updated 2018)

	
Low risk review
 
Applies to 'low risk research' as defined in the National Statement on Ethical Conduct in Human Research 2007 (updated 2018) (referred to hereafter as National Statement). Research timetables should allow for the possibility that a project submitted as a low risk application may be deemed to involve more than low risk, or to raise other issues, therefore requiring full review. Researchers may be requested to provide additional information.

**SECTION 1: PROJECT AND RESEARCHERS' DETAILS**

**1.1 Project title:**

Postural orthostatic tachycardia syndrome (POTS) in Long COVID syndrome: A detailed profiling study (POTS-LCS)

**1.2 Provide a 1-2 sentence plain language summary of the project:**

This summary should be in plain language and suitable for release to the public.

This study aims to define the prevalence of postural orthostatic tachycardia syndrome (POTS) amongst patients with chronic illness post SARS-CoV-2 (COVID-19) infection – also known as Long COVID syndrome (LCS). Critically, this study also aims to unwrap the features of POTS amongst this cohort by looking at the contribution of inflammation, and autoimmunity towards chronic illness. The study will look at clinical biomarkers that may give an understanding of why the virus causes protracted and chronic illness in some people. Understanding of the viral onset of POTS may help guide targeted treatments for both LCS and the associated POTS.

**1.3 Project timeframe:**

Proposed commencement date of activities that require human ethics approval:	March 2021	Estimated completion date of the project:	March 2025
-------------------------------------------------------------------------------------	------------	--------------------------------------------------	------------

Research must not commence without the prior written approval of the HREC. Retrospective approval cannot be provided.

**1.4 If this application is to extend a currently approved project, provide the HREC approval number:**

HREC approval number:	H-2021-053
------------------------------	------------

An [Annual Report on Project Status Form](#) should also be completed.

### 1.8 Has or will this project be submitted for approval to other HRECs?

Include the HREC's name, current status of the application (i.e. submitted, approved, deferred or rejected) and attach this documentation. The University of Adelaide accepts ethics approval granted by some other HRECs and may not require a separate ethics application. Researchers are encouraged to consult with information about [Notification of ethical review and approval from other institutions](#) to see if this applies.

No

### 1.9 Has or will this project be submitted for approval to any departments or institutions?

E.g. Department of Education, prisons, government institutions, or businesses. Attach authorising correspondence and/or approval documentation to the application.

- Yes – the project *will* be submitted for approval to:  
 Yes – the project *has been* submitted for approval to:  
 No

## SECTION 2: NATURE OF THE PROJECT

### 2.1 Aims of the project:

Discuss in standard English the main research aims/hypotheses to be investigated.

The primary objective of this study is to:

[1] Assess the prevalence of POTS in those with LCS, using a standardised and detailed autonomic testing protocol

The secondary objectives of this study include:

[2] Characterising the neuroendocrine/inflammatory/immune biomarker profile of those with LCS(+)/POTS/LCS(-)/POTS and POTS and compare to matched, healthy controls

[3] Determining the impact of LCS with and without POTS and POTS on quality of life & symptom scores, cognitive function and psychological well-being and compare to matched, healthy controls

### 2.2 Rationale of the project:

Explain in standard English the rationale for the project i.e. how the research will fill any gaps or contribute new knowledge to the field.

The prevalence of POTS in sufferers of LCS is unknown, yet symptomatology of both syndromes share many commonalities. Quantifying the presence of POTS in those with LCS will provide significant insight to both the pathogenesis of POTS and the ongoing individual and global health impacts of COVID-19. The study has the potential to detail the incidence of POTS in 'long COVID' sufferers, thereby providing direction for diagnosis and treatment of this significant global cohort. Additionally, the study has the potential to provide understanding of disease pathophysiology in this post-viral syndrome. This will add to the aetiological understanding of the mechanisms of inflammatory and neuroendocrine disturbance in POTS. This work will help improve the diagnosis and management of the many LCS patients with dysautonomia.

### 2.3 Background to the project:

Briefly discuss any previous research of relevance and cite no more than 4 key references.

Long COVID Syndrome (LCS) is a term now frequently utilized to describe the collection of chronic symptoms lingering at  $\geq 3$  months post-acute SARS-CoV-2 infection. Several studies detail the presence of multi-systemic chronic symptoms such as fatigue, reduced cognition, exercise intolerance, pain and tachycardia in this cohort. While much remains unknown regarding LCS, involvement of the autonomic nervous system has been suggested.

The Office for National Statistics, UK have found that as many as 1 in 10 individuals are likely to suffer these symptoms post SARS-CoV-2 infection consistent with LCS. With more than 108 million global cases of SARS-CoV-2 infection (as of February 13th 2021, Johns Hopkins Coronavirus Resource Center), there are potentially a high burden of LCS cases. Consequently, detailed characterization of this cohort of LCS patients is important as a high proportion of these individuals remain symptomatic with significant disability and unable to return to work.

Postural orthostatic tachycardia syndrome (POTS) is a heterogenous disorder characterized by chronic and disabling symptomatology that predominately affects young women of child bearing age. POTS onset has a reported association with antecedent viral illness as well as concomitant autoimmune disease. Onset of this multisystemic disorder has been described in a recent case report after SARS-CoV-2 infection. The pathophysiology remains unknown but may include post-viral autoimmunity, increased central sympathetic outflows, deconditioning/hypovolemia or neuro-endocrine related. Indeed, inflammatory biomarkers and

adrenergic and cholinergic antibodies have been reported in POTS and are of interest in the pathogenesis of post viral onset of this syndrome and the interplay with inflammatory pathways and neuroendocrine dysfunction.

While urine frequency and nocturia are frequently reported in POTS, these symptoms have generally been attributed to dys-innervation of the bladder similar to that experienced in an overactive bladder. There is little in the way of research to establish whether those with POTS are experiencing true polyuria (>50 ml/kg 24hrs) or whether they are experiencing frequency and urgency as a result of dys-innervation of autonomic control of the bladder. Anecdotally, some with Long Covid describe a similar experience of periods of polyuria with associated cardiac symptomology. Establishing the underlying aetiology of polyuria and nocturia in these cohorts is crucial for identifying effective treatment options and important for improved understanding of contributing pathogenesis of LCS and POTS.

Previous animal models have demonstrated that increased renal bradykinin expression results in increased polyuria compensated by reflex polydipsia. These studies also echoed the paradoxical finding of reduced plasma renin in the presence of established hypovolaemia previously noted in POTS cohorts. The animals in these studies underwent several alterations to normal cardiovascular function similar to those characterised in POTS. Namely: excessively increased orthostatic heart rate, decreased heart rate variability, decreased LF/HF ratio and a paradoxically unchanged MAP and only slightly raised systolic BP. This raises the consideration that inflammatory responses may play a role in disruption of the neuroendocrine feedback system that maintains fluid balance, resulting in hypovolaemia and cardiac augmentation. Additionally, others have reported elevated G-protein-coupled receptor antibodies in POTS cohorts and animal models and have demonstrated that presence of these autoantibodies' elicits symptoms of orthostatic intolerance, including cardiac augmentation.

This study will provide insight into the interplay of inflammation, neuroendocrine function and dysautonomic control of heart rate and blood pressure that leads to the debilitating presence of POTS and/or LCS. Additionally, Delineating the prevalence of POTS in the LCS patients may help improve the diagnosis and management of this growing entity given the unprecedented global pandemic.

**2.4 Have there been any preliminary studies? If YES, provide the project title and HREC approval number(s):**

Accompanying submission for Oz-POTS registry which will be drawn on for recruitment of POTS patients for this study.

**2.5 Research methodology:**

Describe how the study will be undertaken and explain what interactions will occur between researchers and participants. Include a description of the research methodology and how this will achieve the research aims. For example, you could include a justification of why the sample size/sampling method will yield valid and reliable results. Where appropriate, please refer back to the aims described in 2.1 when describing the methodological approach.

We plan to enrol 218 participants for this study (n= 150 with LCS, n=34 with POTS, n = 34 healthy matched controls). Subjects who meet the inclusion and none of the exclusion criteria and who provide informed consent, will be invited to attend in person to facilitate physical examination including autonomic testing, blood draw and associated investigations (see table below). The comprehensive nature of this exercise will allow subjects to complete various tools/questionnaires at their leisure via online portal links to a secure REDCap database, to reduce the impact of fatigue on the accuracy of findings.

**Subject preparation:**

48 hr before examination the following will be discontinued

- Anticholinergics
- Sympathomimetics ( $\alpha$  and  $\beta$  agonists)
- Mineralcorticoids (Fludrocortisone)

24hr before examination the following will be discontinued

- Alcohol
- Salt tablets
- Caffeine
- Beta Blockers (propranolol, metoprolol), Ivabradine, Calcium channel blockers

[figure not shown]
8 hrs before testing

- Fast from food
- Drink only water 'to thirst' and abstain from fluid 'loading'

On the morning of testing

- No wearing of compression wear
- No abdominal binders
- No support stockings

Figure 1: Project Schema

As participants in this study are excluded from having other significant cardiac impairments or significant medical conditions, it is unlikely that drug cessation will cause any detriment other than the discomfort and inconvenience of poorly controlled orthostatic intolerance. Participants will be encouraged to discuss cessation of medications with their regular doctor. In addition, senior clinician researchers will identify those in the screening process who may have increased risk if medications are ceased. If it is decided that individuals are unable to cease the above listed medications for the prescribed time, then those participants will not be able to participate in the study. This is the case because biomarker and autonomic testing outcomes would not be deemed meaningful in the setting of artificial control of heart rate and fluid status.

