### 3.3 What is the number of participants?

Cohort One (LCS): 150 consecutive patients with LCS will be recruited from various social media and LCS support group platforms.

Cohort Two (POTS) 34 consecutive patients with POTS will be recruited from a speciality POTS clinic run by [name] who is an Assoc/Prof at The University of Adelaide, Centre for Heart Rhythm Disorders

Cohort Three (Controls): 34 healthy, matched age and gender controls will be recruited from University and private medical campuses.

A base sample size calculation can be made using the formula:  $n = (t^2 \times p(1-p)) / m^2$ , where  $t$ =confidence level at 95%,  $p$ =estimated prevalence of POTS within an LCS sample and  $m$  is the relative precision. Using this formula, a sample size of 139 provides sufficient statistical power to estimate a proportion (10% POTS amongst LCS) with a precision of 5% at the 95% confidence level. The number is increased to 150 to allow for withdrawal from the study.

From Walker et al. 2013 paper, the following information was obtained: at 30 minutes of orthostatic time, Stand healthy group (N=15) had mean orthostatic change in heart rate 26 bpm + SE=4 (SD=SE\*SQRT(N) = 15.5) and the Stand POTS group (N=15) had mean orthostatic change in heart rate 45 bpm + SE=5 (SD=SE\*SQRT(N) = 19.4). Using a two-sample Satterthwaite t Test assuming unequal variance, with alpha=0.05, two-sided test and SD=15.5 and 19.4, it was found that there was 80% power to detect a mean difference of 45-26=19 when using a sample size of N=15 per group. If there is expected to be 20% loss to follow up, then a total of  $(20/9)*30=66.66$  so N=34 is required in each group (N=68 in total) The statistical software used was SAS 9.4 (SAS Institute Inc., Cary, NC, USA).

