#### 4.1 Describe the likely burdens of participation and any risks to participants when undertaking the research:

Burdens include impacts on participants such as inconvenience e.g. filling in a form, participating in a street survey, or giving up time to participate in research and discomfort e.g. minor side-effects of medication, the discomforts related to measuring blood pressure, and anxiety induced by an interview. Risks can be emotional, social, legal, medical or physical and can include distress and harm. See *National Statement Chapter 2.1*.

Participation in the POTS-LCS involves potential risks of a breach of confidentiality of medical information and privacy of the participants.

As many participants will be known to the researchers, consideration must be given to the potential for participants feeling ‘obligated’ to participate in the study.

Some of the investigations such as blood samples and 24hr Holter monitors may cause some discomfort and inconvenience.

Orthostatic challenge tests may illicit symptoms such as dizziness and palpitations particularly in those with POTS. In susceptible patients, vasovagal syncope may occur, in which case the test will be terminated immediately, the patient offered medical assistance and then arrangements made for safe return home (arranging a family member to pick them up or providing a taxi home)

Some participants will be required to cease medications that currently control heart rate and reduce the effects of POTS on orthostatic intolerance. Those with a serious heart condition are excluded from this study therefore, medication that participants are currently on does not control a serious underlying cardiac condition but rather ‘improves’ functionality and quality of life related to POTS/Long Covid. It is likely that those on these medications will experience a decline in functionality and an increase in unpleasant orthostatic intolerance symptoms during the period of medication cessation.

Reimbursement for any reasonable travel, parking, and other expenses associated with the research project visit will be provided up to \$30.

Quality of life questionnaires have the potential to trigger emotional responses particularly for those who are confronted by chronic illness.

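### The rule barring LCS volunteers who cannot stop listed drugs can remove POTS cases from the primary prevalence, and nothing in the protocol records who is turned away

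*Protocol*

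**What the plan says.** Section 2.1 sets the primary objective: "Assess the prevalence of POTS in those with LCS, using a standardised and detailed autonomic testing protocol". Section 3.3 describes the sample for it: "150 consecutive patients with LCS will be recruited from various social media and LCS support group platforms". The calculated 139 is raised to 150 to cover withdrawals.

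Subject preparation, in Section 2.5, lists drugs and other items to be stopped 48 or 24 hours before testing. At screening, "senior clinician researchers will identify those in the screening process who may have increased risk if medications are ceased". If individuals are then judged "unable to cease the above listed medications for the prescribed time, then those participants will not be able to participate in the study". The reason given is that "biomarker and autonomic testing outcomes would not be deemed meaningful in the setting of artificial control of heart rate and fluid status". The rule is not limited to the POTS cohort.

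Section 4.1 says what the drugs are for: "Some participants will be required to cease medications that currently control heart rate and reduce the effects of POTS on orthostatic intolerance". It adds that participants' medication "does not control a serious underlying cardiac condition but rather" serves function and quality of life in POTS or Long Covid. Section 4.2, under Discomfort and Inconvenience, says that the symptoms returning after cessation can be serious for certain people.

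The exclusion list in Section 3.6 does not contain the rule. Section 3.7 acknowledges selection bias, but only from social-media recruitment.

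**The concern.** The stated reason for the rule is a reason not to test people while they are on these drugs. It does not settle how a prevalence estimate should account for them. The primary result is a proportion, and entry to it depends partly on a treatment that the protocol itself links to the condition being counted. An LCS volunteer who takes none of the listed drugs cannot be removed by this rule. One who takes them for orthostatic symptoms can be.

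If POTS cases are turned away more often than non-cases, the reported prevalence is too low, and enrolling more people does not correct it. The protocol describes no record of those turned away for this reason. A later analysis plan cannot recover people whom screening never recorded, so this is a data-capture gap as well as an analysis question.

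**Working it through.** **The plan's own figure.** Section 3.3 uses n = z²p(1−p)/m². With z = 1.96, p = 0.10 and m = 0.05 (absolute), n = 3.8416 × 0.09 / 0.0025 = 138.3, rounded up to 139. This reproduces. The 95% half-width is 4.99 points at n = 139 and 4.80 points at n = 150.

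**Effect of the rule.** Let P be the true prevalence among otherwise eligible LCS volunteers, e1 the share of POTS cases the rule excludes, and e0 the share of non-cases it excludes. Then

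observed prevalence = P(1−e1) / [P(1−e1) + (1−P)(1−e0)].

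P = 10% comes from Section 3.3. The protocol gives neither e1 nor e0, so the values below are assumptions.

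| e1 (cases lost) | e0 (non-cases lost) | Calculation | Observed prevalence |
|---|---|---|---|
| 5% | 0% | 0.095 / 0.995 | 9.5% |
| 10% | 0% | 0.090 / 0.990 | 9.1% |
| 20% | 2% | 0.080 / 0.962 | 8.3% |
| 30% | 5% | 0.070 / 0.925 | 7.6% |
| 50% | 5% | 0.050 / 0.905 | 5.5% |
| 10% | 10% | 0.090 / 0.900 | 10.0% (no bias) |
| 5% | 10% | 0.095 / 0.905 | 10.5% (upward) |

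The bias is downward only when e1 exceeds e0.

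**Loss needed for a given error.** With e0 = 0, solving for the loss that gives observed prevalence o yields e1 = 1 − o(1−P) / [P(1−o)]:

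- 1 point (o = 9%): 1 − 0.081/0.091 = 11% of cases
- 2 points (o = 8%): 1 − 0.072/0.092 = 22% of cases
- 5 points (o = 5%): 1 − 0.045/0.095 = 53% of cases

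**Higher prevalence.** At P = 30% with e1 = 20% and e0 = 5%, the observed value is 0.24 / 0.905 = 26.5%, a fall of 3.5 points.

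**What bounds would show.** Suppose 15 cases are found in 150 tested, and 10 further LCS volunteers were excluded only for medication. The tested-only estimate is 15/150 = 10.0%. With the 10 counted as having no POTS it is 15/160 = 9.4%. With all 10 counted as POTS it is 25/160 = 15.6%.

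**Sections side by side.** Section 2.5 invites those who meet the inclusion criteria and none of the exclusion criteria. Subject preparation then adds a ground for non-participation that Section 3.6 does not list. The nearest entry there, being unavailable for all assessments, is a different matter.

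**The case against.** The strongest reply is that differential loss is not shown and may be small. Cessation lasts only 24 to 48 hours, and the protocol says "it is unlikely that drug cessation will cause any detriment other than the discomfort and inconvenience of poorly controlled orthostatic intolerance", which points to few exclusions. The screening concern is increased risk on stopping, not severity of orthostatic tachycardia. People at increased risk are only identified at that step; they leave only if it is decided that they cannot stop. The list also includes anticholinergics, sympathomimetics and calcium channel blockers without stating why LCS volunteers would take them. The Section 4.1 statement about medication covers some participants across all cohorts, including 34 people recruited because they have POTS. All of this stands, and it limits the claim to what the rule can do.

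A reader might infer that most LCS volunteers on these drugs are POTS cases, so that the rule must bias prevalence downward. The documents do not support that: they give no rates, and equal or greater loss of non-cases would leave no bias or reverse it. The overall direction is open too, because LCS recruitment runs through support groups with an advert that names POTS (Attachment 4).

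A second objection is that sensitivity analyses and reporting of exclusions usually belong in a statistical analysis plan, which is not shown. That holds for the analysis itself. It does not hold for capturing the data at screening, without which no such analysis is possible.

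A third is that adding POTS status from past records would mix methods of ascertainment. Section 2.1 specifies standardised testing, and Section 3.15 leaves analysis of medical records unticked. This also stands, and the fix does not merge such records into the estimate.

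**Conclusion.** The concern holds as a possibility that the protocol itself creates and does not acknowledge. A stated rule can remove LCS volunteers from the primary proportion in a way related to the outcome. Downward bias follows if, and only if, cases are excluded at a higher rate than non-cases.

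The size cannot be computed from the documents. At the planned 10% prevalence, and with the extreme assumption that no non-cases are lost, the error stays within the 5-point precision target unless about 53% of cases are excluded.

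It would be tempting to cite a larger example: at 30% prevalence, losing one third of cases turns 45/150 into 30/135 = 22.2%, an error of 7.8 points. That does not show a clear breach of the planned precision. The 5-point margin was derived at 10%; at 30% with n = 150 the half-width is 1.96 × √(0.21/150) = 7.3 points, and the one-third loss is itself an assumption.

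The point is worth acting on because the remedy is cheap and the information is lost if it is not recorded at screening. No view is taken on the cessation rule.

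**What to change.** Leave the cessation rule and the exclusion from testing unchanged, and keep the tested-only prevalence as the primary estimate. Then:

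- At screening, log each LCS volunteer who is otherwise eligible but excluded only for medication, with the drug and any self-reported prior POTS diagnosis. Use the self-report for description, not to assign case status.
- Report the number excluded for this reason beside the primary result.
- Give sensitivity bounds with these people added to the denominator, once as all POTS and once as none.
- Reconcile Subject preparation with the exclusion list in Section 3.6, so that it is clear whether inability to stop the listed drugs is a formal exclusion criterion.
- Mention this source of selection in Section 3.7 with the recruitment bias already acknowledged there.

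The cost is one field in the screening log, short consent wording for keeping the screening data, and a wider reported range for the prevalence. No testing is added.

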### Study testing day:

The following testing protocol will take approximately 60-90 minutes to complete. A schematic representation of the protocol can be seen (Figure 1: above)

Non-invasive measurements of continuous arterial pressure and heart rate will be obtained using finger photoplethysmography (non-invasive blood pressure testing; NIBP) for 5 minutes before testing (rest) and then during each reflex test. This involves application of a small cuff to either of the 2nd to 5th digits of

one hand. The cuff is inflated to allow measurement of finger arterial blood pressure. This technique is well validated in a variety of clinical and experimental conditions and is similar to our prior protocol. Description of each test can be found in section 3.16

Testing variables	Cohort 1	Cohort 2	Cohort 3
Demographic Survey	X	X	X
Medical health history	X	X	X
Medications use	X	X	X
Physical examination	X	X	X
Health Related QoL			
- SF-36 [36-Item Short Form Survey]	X	X	X
- EQ-5D [5 level EQ score]	X	X	X
- COMPASS-31 [composite autonomic symptom scale]	X	X	X
- FSS [fatigue severity score]	X	X	X
- 5 Point hypermobility screen	X	X	X
- OHQ [orthostatic hypotension questionnaire]	X	X	X
Autonomic testing			
- Standing test, deep breathing, Valsava manoeuvre	X	X	X
- Sudomotor function (SUDOSCAN)	X	X	X
- 24-hour Holter monitoring	X	X	X
- Echocardiogram with Passive Leg Raise	X	X	X
Blood tests:			
- Complete Blood Panel and Electrolytes, CRP, ESR,	X	X	X
# TNF- $\alpha$ , IL-6, IL-1 $\beta$ , IL-10, IL-21, INF $\gamma$ , INF $\alpha/\beta$ , CD30,	X	X	X
# $\alpha$ 1 adrenergic, Beta-1 adrenergic, M1 and M4 muscarinic	X	X	X
cholinergic receptor Ab;			
# Aldosterone, Potassium, Renin activity, copeptin level;	X	X	X
# Plasma Histamine, heparin, chromogranin A	X	X	X
24 hr Urinary volume and osmolarity	X	X	X
Cognitive and psychological testing			
- CANTAB (Cambridge neuropsychological test automated battery)	X	X	X
- HADS (hospital anxiety and depression scale)	X	X	X

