# Are You a Healthy Adult Willing to Volunteer for a Study Exploring 'Long Covid'?

**The University of Adelaide, Centre for Heart Rhythm Disorders are looking for men and women to participate in a research study to evaluate the cardiovascular, immune and inflammatory causes of 'Long Covid'.**

To qualify, participants in this study will be men and women who:

- ❖ Are 18 years or over
- ❖ Have no other significant illnesses
- ❖ Do not take regular medication apart from the contraception pill

**Please email [[contact]](mailto:[contact]) for more information and to find out if you are eligible to participate in the study.**

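### Inflammatory, immune and histamine contrasts with controls are open to confounding by treatment: drugs acting on these markers are neither stopped nor excluded in patients, while controls are sought as unmedicated

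*Protocol*

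**What the plan says.** **Stopping list.** Section 2.5, Subject preparation, has two tiers. The first ("48 hr before examination the following will be discontinued") covers anticholinergics, sympathomimetics and mineralocorticoids. The 24-hour tier covers "Beta Blockers (propranolol, metoprolol), Ivabradine, Calcium channel blockers", along with alcohol, caffeine and salt tablets. People who cannot stop these are not enrolled, because "biomarker and autonomic testing outcomes would not be deemed meaningful in the setting of artificial control of heart rate and fluid status".

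**Markers.** The testing table in section 2.5 applies to all three cohorts. Besides renin, aldosterone and copeptin it includes "Complete Blood Panel and Electrolytes, CRP, ESR", a cytokine and immune panel (TNF-α, IL-6, IL-1β, IL-10, IL-21, interferons, CD30), receptor antibodies and "Plasma Histamine, heparin, chromogranin A".

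**Use of the markers.** Secondary objective 2 in section 2.1 is "Characterising the neuroendocrine/inflammatory/immune biomarker profile of those with LCS(+)/POTS/LCS(-)/POTS and POTS and compare to matched, healthy controls".

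**Who may be medicated.** The exclusions in section 3.6 name conditions, surgery and addiction but no prescribed drug class. Section 3.1 describes the POTS cohort as patients already treated for POTS. The LCS cohort has at least three months of chronic illness. For controls, the Attachment 5 notice asks for healthy people who take no medicines, and the flyer asks for people who "Do not take regular medication apart from the contraception pill". Section 3.16 has controls checked on attendance for excluded medications.

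**Analysis.** Section 5.5 gives summary statistics, chi-square or Fisher tests for categorical variables, and two-sided p < 0.05. It names no test or model for continuous markers. Medication use is recorded in all cohorts.

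**The concern.** The protocol accepts that drug effects can make a biomarker result meaningless, then acts on this for only part of its panel. Corticosteroids other than the listed mineralocorticoids, anti-inflammatories, immunomodulators, antihistamines and acid suppressants can be expected on general pharmacology to move one or more of the remaining markers. Nothing in the preparation or exclusion rules limits them in patients, and the recruitment material steers such users away from the control group.

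Matching on age and gender does not remove an imbalance of this kind, and a larger sample does not shrink it. A drug that lowers a marker could hide a real elevation; one that raises it could create an apparent elevation. The contribution of inflammation and autoimmunity is put forward in the plain-language summary (section 1.2) as a central aim, so attribution of these differences to disease matters to how the study will be read.

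**Working it through.** **1. The protocol's own figures.** Section 3.3 sizes two other questions, and both figures reproduce.
- Prevalence: 1.96² × 0.10 × 0.90 / 0.05² = 138.3, rounded up to 139.
- Heart-rate change: Satterthwaite t test, difference 19, SDs 15.5 and 19.4, 15 per group, power 0.815 against the stated 80%.

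No figure is given for any biomarker contrast, so neither result bears on this point.

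**2. Stopping list against marker panel.**

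| Measured in all cohorts | Addressed by the stopping list? |
|---|---|
| Autonomic tests | Yes |
| Renin, aldosterone, copeptin | Yes (fluid status) |
| CRP, ESR, cytokines, CD30 | No listed item is aimed at these |
| Histamine, chromogranin A | No listed item is aimed at these |

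The exclusion criteria do not fill the gap, since they name no drug class of this kind.

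**3. Size of the bias, on assumed inputs.** The protocol gives neither the share of patients using such drugs nor the drug effect. Let f be the share of LCS participants on a drug acting on a given marker, e the shift in SD units, and let controls be untreated. Then bias = f × e, and the variance among patients becomes 1 + f(1 − f)e². Group sizes are 150 and 34 (section 2.5), two-sided 5% (section 5.5). The last column is a normal approximation with no true disease difference.

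| f | e (SD) | Bias (SD) | Rejection rate, no true difference |
|---|---|---|---|
| 0.20 | 0.5 | 0.10 | 8% |
| 0.20 | 1.0 | 0.20 | 18% |
| 0.40 | 0.5 | 0.20 | 18% |
| 0.40 | 1.0 | 0.40 | 54% |

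A simulation with the Welch t test gave 7.6% to 52% over the same range.

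**4. Masking of a real difference.** Take a true elevation of 0.53 SD, chosen because 150 v 34 has about 80% power for it (two-sample t test: 0.79). A marker-lowering drug leaves 0.53 − bias to be detected:
- bias 0.1: 0.43 SD, power 0.61
- bias 0.2: 0.33 SD, power 0.41
- bias 0.4: 0.13 SD, power 0.10

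**5. Cost of repeating without exposed participants.** Removing 20% or 40% of 150 leaves 120 or 90 LCS participants. Power for 0.53 SD against 34 controls is then 0.77 or 0.74, compared with 0.79. At the same rates POTS falls from 34 to about 27 or 20. The LCS participants with POTS, expected at 10% × 150 = 15, fall to 12 or 9.

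**The case against.** **Section 5.5 prescribes no unadjusted analysis.** A reader might infer that the plan commits to a plain group comparison and gives the medication data no role. It does not: it is silent on continuous markers, and a separate analysis plan may deal with medication. That objection stands against any claim that the stated analysis is wrong. It does not remove the point, because the imbalance comes from the preparation, exclusion and recruitment text. If last-dose timing is not captured (the protocol does not say), no later plan can recover it.

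**The separation of cohorts is softer than it looks.** The control restriction sits in advertisements, not in the control criteria of section 3.6. The check in section 3.16 refers to excluded medications that section 3.6 never lists. The flyer speaks of regular use only. On the patient side, no text says that anyone takes these drugs; they are simply not prohibited. This stands, and it is why the contrasts are called open to confounding rather than confounded.

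**The quoted rationale is not itself false.** It explains why people who cannot stop the listed drugs are not enrolled, and fluid status does matter for some of the biomarkers. It does not claim that no other drug affects any marker. The difficulty is that its logic is not carried through to the rest of the panel.

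**All magnitudes are assumed.** This stands. For a given marker, f must be the share on a drug acting on that marker, so several drug classes cannot be pooled into one rate. With marker-lowering drugs the false rejections would mostly show LCS below controls, so they should not be read as spurious evidence of inflammation in LCS.

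**The work is secondary and exploratory.** True, and the biospecimen appendix says so. That limits the weight of the point, not its validity.

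**Conclusion.** The point holds for the patient-control contrasts on CRP, ESR, cytokines, histamine and chromogranin A under secondary objective 2. As written, the rules allow marker-altering treatment to be common in patients and rare in controls, so a difference, or the lack of one, could not safely be attributed to disease.

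The bias is 0.1-0.4 SD if 20-40% of LCS participants take a drug shifting the marker by 0.5-1.0 SD and controls take none. Both ranges are assumptions, and the true size is unknown and could be negligible.

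A reader might infer that the study's main result is compromised. The documents do not support that: this point does not touch the prevalence of POTS in LCS, and the stopping list does address the autonomic tests and the fluid-regulating hormones.

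**What to change.** **In section 5.5**, state that each immune, inflammatory and mast-cell marker contrast will be:
1. reported for the full cohorts;
2. repeated after excluding participants with current or recent use of a drug class acting on that marker, with the classes and the meaning of recent fixed before the data are examined;
3. accompanied by a table of the share of each cohort using each class.

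**On the medication form**, add a date of last dose.

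Regression adjustment should not be relied on for the patient-control contrasts. With controls nearly drug-free there is little overlap, and the drug effect would have to be estimated among patients, where use may follow severity. It may be used for contrasts among the patient groups.

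**Cost.** Analysis wording, one form field and one table. The repeat analysis is smaller: on the assumed rates it loses 2 to 5 points of power for LCS v controls, and the POTS and LCS-with-POTS groups become thin. Excluding users may also select milder patients, so the two results should be shown side by side.

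The sponsor should reconcile the stopping list with its stated biomarker rationale, and the control medication check in section 3.16 with the exclusions in section 3.6. No change to what participants stop is proposed here.
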